- A concentration average will be plotted for a given sampling time only if 2/3 of the individual data at the time point have quantifiable measurements that are within the sampling time window specified in the protocol or $\pm 10\%$. An average concentration estimated with less than 2/3 but more than 3 data points may be displayed on the mean concentration plot if determined to be appropriate and will be documented within the final study report.

Treatment of Outliers during Pharmacokinetic Analysis

Application of this procedure to all PK analyses is not a requirement. Rather, this procedure provides justification for exclusion of data when scientifically appropriate. This procedure describes the methodology for identifying an individual value as an outlier for potential exclusion, but does not require that the value be excluded from analysis. The following methodology will not be used to exclude complete profiles from analysis.

Data within an Individual Profile

A value within an individual profile may be excluded from analysis if any of the following criteria are met:

- For PK profiles during multiple dosing, the concentration of the pre-dose sample exceeds all measured concentrations for that individual in the subsequent post-dose samples.
- For PK profiles during single dosing of non-endogenous compounds, the concentration in a pre-dose sample is quantifiable.
- For any questionable datum that does not satisfy the above criteria, the profile will be evaluated and results reported with and without the suspected datum.

Data between Individual Profiles

1. If $n \geq 6$, then an objective outlier test will be used to compare the atypical value to other values included in that calculation:
 - a. Transform all values in the calculation to the logarithmic domain.
 - b. Find the most extreme value from the arithmetic mean of the log transformed values and exclude that value from the dataset.
 - c. Calculate the lower and upper bounds of the range defined by the arithmetic mean $\pm 3 \times SD$ of the remaining log-transformed values.

- d. If the extreme value is within the range of arithmetic mean $\pm 3*SD$, then it is not an outlier and will be retained in the dataset.
- e. If the extreme value is outside the range of arithmetic mean $\pm 3*SD$, then it is an outlier and will be excluded from analysis.

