If the remaining dataset contains another atypical datum suspected to be an outlier and $n \geq 6$ following the exclusion, then repeat step 1 above. This evaluation may be repeated as many times as necessary, excluding only one suspected outlier in each iteration, until all data remaining in the dataset fall within the range of arithmetic mean $\pm 3*SD$ of the log-transformed values.

Reporting of Excluded Values

Individual values excluded as outliers will be documented in the final CSR. Approval of the final CSR will connote approval of the exclusion.

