10.3.2 Pharmacokinetic Statistical Methodology

No formal statistical analysis is planned for this study. The PK parameters will be listed and summarized by study week using standard descriptive statistics. Insert stats methodology here.

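### SAP 10.3.1 gives two conflicting rules for between-participant PK outliers, and the mandatory one drops values with no documented cause and no with/without summary

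*SAP*

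**What the plan says.** All of this is in SAP 10.3.1 unless noted.

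- **Introduction to the outlier procedure.** Applying it to every PK analysis is optional; "this procedure provides justification for exclusion of data when scientifically appropriate". It identifies candidates for exclusion but "does not require that the value be excluded from analysis". It may not be used to remove whole profiles.
- **Between participants, step 1.** With at least six values, "an objective outlier test will be used to compare the atypical value to other values included in that calculation". The most extreme log value is set aside, and the mean and SD are computed from the rest.
- **Step (e).** If the value lies outside mean ± 3 SD of the rest, "then it is an outlier and will be excluded from analysis".
- **Repeat.** "If the remaining dataset contains another atypical datum suspected to be an outlier", and at least six values remain, the test is run again, one value at a time.
- **Within a profile.** For a questionable value that meets neither listed criterion, "the profile will be evaluated and results reported with and without the suspected datum".
- **Reporting.** "Individual values excluded as outliers will be documented in the final CSR"; approving that report counts as approving the exclusion.
- **Output (SAP 10.3.2).** "The PK parameters will be listed and summarized by study week using standard descriptive statistics". SAP 10.1 adds the geometric mean and geometric CV% for AUC and Cmax.

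**The concern.** The introduction makes exclusion a matter of judgement; step (e) makes it automatic. The SAP does not rank them, and it defines neither what makes a value atypical enough to test nor when exclusion is appropriate. The study is open-label and SAP 11 allows ongoing access to PK data, so the choice to run the test can be made with the values known.

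There is no hypothesis test. The descriptive summaries of AUC over 0 to 4 weeks, steady-state Cmax and steady-state AUC are the primary result, and Protocol 4.3 will use the observed exposure to judge linearity against 700 to 2800 mg. A rule that trims the tails makes between-participant variability look smaller than it is.

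The effect of treatment-emergent anti-drug antibodies (TE-ADA) on PK is an exploratory objective (Protocol 3). An extreme exposure may be the signal sought, and the SAP does not say whether exclusions carry into the ADA-PK displays of 10.4.7.

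**Working it through.** The documents state no exclusion rate, so there is no plan figure to reproduce. From the SAP: the rule, and about 40 enrolled with about 25 completing (SAP 8). Assumed: log-normal data, and a CV of 25% where a CV is needed (log SD = √ln(1 + 0.25²) = 0.246).

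**1. Effective limit.** The SD excludes the suspect value, so 3 SD of the rest is a tighter limit in terms of all the data. Let s be the SD of all n values and r the SD of the rest. At the limit the value lies 3r from the mean of the rest, so:

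- distance from the overall mean = 3r(n-1)/n
- (n-1)s² = (n-2)r² + 9r²(n-1)/n

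n = 25: s² = (23 + 8.64)/24 r² = 1.318r², s = 1.148r; limit 2.88/1.148 = **2.51 SD**.
n = 40: s² = (38 + 8.775)/39 r² = 1.199r², s = 1.095r; limit 2.925/1.095 = **2.67 SD**.

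**2. Chance of dropping a valid value.** A value fails when its deleted t statistic (n-2 degrees of freedom) exceeds 3√((n-1)/n) in size. The per-value probability is 0.00736 at n = 25 and 0.00524 at n = 40. Upper bounds: 25 × 0.00736 = 0.184; 40 × 0.00524 = 0.210.

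Simulation of steps a to e with the repeat, on clean data (40,000 runs per n):

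| | n = 25 | n = 40 |
|---|---|---|
| At least one value dropped | 18.1% | 20.3% |
| Log SD ratio when dropped | 0.810 | 0.871 |
| Log SD ratio when dropped, no repeat | 0.837 | 0.891 |
| Geometric CV when dropped | 24.7% to 19.9% | 24.8% to 21.6% |
| Log SD ratio, all data sets | 0.966 | 0.974 |
| Geometric mean shift | -0.008% | +0.007% |

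The drop rates and log SD ratios do not depend on the assumed CV.

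**3. Dependence on use.** The table applies the test to every summary. If it is never applied, the rate is 0%. If only values beyond 3 SD of all the data are tested (an assumed trigger), it is 2.0% at n = 25 and 5.8% at n = 40.

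**4. If ADA alters exposure.** All inputs are assumed: n = 25, CV 25%, affected participants with 60% lower exposure, repeat rule, 6,000 runs per cell.

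| Affected | Chance a minority-group value is removed | Geometric mean shift |
|---|---|---|
| 2 | 78% (low) | +5.5% |
| 5 | 19% (low) | +1.4% |
| 8 | 2% (low) | +0.1% |
| 12 | 0% | 0.0% |
| 17 | 2% (high) | -0.1% |
| 20 | 18% (high) | -1.3% |
| 23 | 78% (high) | -5.2% |

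With 2 and 23 affected, 50% lower exposure gives +2.5% and -2.4%; 30% lower gives +0.3% and -0.3%. At 60% lower, CV 20% gives +7.0% and -6.5%, and CV 35% gives +3.0% and -2.9%. The rule removes whichever group is the small minority, so the sign depends on how many are affected.

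**The case against.** The best defence is that the introduction covers everything below it: the procedure is optional, and step (e) only states the outcome once someone has chosen to apply it. On that reading the fault is one word, *will* for *may*. But the introduction says that the method itself does not oblige exclusion, so the conflict remains even after the test has been invoked, and the choice to invoke it has no defined trigger.

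Safeguards exist. Whole profiles stay, exclusions and special handling are documented in the study report, and individual parameters are listed, so a reader could recompute a summary. Values of AUC to infinity and half-life left out of summaries are footnoted on the table, but the SAP promises no such footnote for the three primary parameters. The table shells are a separate document not available here and might show both versions; the supportable claim is that the SAP text does not require it.

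On size, the objection largely stands. The 18% and 20% are ceilings, the average fall in log SD is only about 3% even then, and no test or threshold depends on it. The ADA case rests on assumed inputs. The 92.2% TE-ADA in Protocol 2.2 comes from patients in earlier studies and measures antibody presence, not altered exposure. It shows only that a mostly affected sample cannot be ruled out.

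On scope, step 1 refers to a single calculation and 10.4.7 plots observed troughs and individual clearance. That suggests, but does not state, that exclusions would not carry over.

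Finally, saying which clause governs would cure the contradiction. It would not cure the substance: if step (e) governs, valid values are dropped automatically; if the introduction governs, the decision stays open after the data are seen.

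**Conclusion.** The concern holds. The wording conflict, the absence of any required cause and the lack of a with/without requirement for between-participant values are plain from the text.

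The main consequence is an understated geometric CV%: by roughly a fifth at n = 25 when a value is dropped, in at most about 18% of summaries there and 20% at n = 40. The realised frequency is unknown and may be nil. With no true outliers the geometric mean is unaffected; a shift needs a real subgroup difference, whose size and frequency the documents do not give. This does not invalidate the study, but it should be corrected before the PK summaries are produced.

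**What to change.** Replace step (e) with wording such as:

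> A value outside the range will be flagged and investigated. It stays in the primary PK summaries unless there is a documented assay, dosing or sampling error. Where any value is flagged or excluded, summaries will be shown with and without it. Exposure that is high or low relative to other participants, including by ADA status, is not by itself a reason for exclusion.

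Align the repeat rule with this, and state that the ADA-PK displays in 10.4.7 keep every value without a documented error. At the very least, state whether the introduction or step (e) governs.

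The cost is SAP wording and one sensitivity column. The reported CV% may be slightly larger. The change extends the SAP's own within-profile safeguard to values compared between participants.

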10.3.2 Pharmacokinetic Statistical Methodology

No formal statistical analysis is planned for this study. The PK parameters will be listed and summarized by study week using standard descriptive statistics. Insert stats methodology here.

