2.1. Study Rationale

Study I5T-MC-AACP (AACP) will investigate the pharmacokinetics (PK) and safety of intravenous (IV) administration of donanemab in healthy participants every 2 weeks (Q2W) for 10 weeks at a 350-mg dose to support dosing regimens in future studies.

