4.3. Justification for Dose

Donanemab 350 mg IV Q2W was selected for this study because this dose is within the dose range previously evaluated in Phase 1 and Phase 2 studies. A 350 mg dose of donanemab administered as a single IV dose is within the dose range previously evaluated in Phase 1 studies (Studies AACC and AACD). In Study AACC, doses of 0.1 mg/kg, 0.3 mg/kg, 1 mg/kg, 3 mg/kg, and 10 mg/kg (equivalent to approximately 7 mg, 21 mg, 70 mg, 210 mg, and 700 mg, respectively) of donanemab were assessed. Doses at or below 3 mg/kg (210 mg) had lower than dose proportional exposure (with half-life ~ 4.7 days) whereas exposure following the single doses of donanemab between 10 mg/kg (700 mg) and 40 mg/kg (2800 mg) were shown to be dose proportional (with half-life of 11 days) in Study AACD.

Observed exposure following a 350-mg dose of donanemab from this study will assess whether this exposure falls within linear or nonlinear exposure range compared with a 700- to 2800-mg dose range.

In participants with MCI due to AD or mild to moderate AD, including Japanese and non-Japanese, the following doses were generally well tolerated:

- up to 40 mg/kg, that is approximately 2800 mg as a single dose, and
- up to 20 mg/kg, that is approximately 1400 mg as multiple doses administered Q4W.

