8.9. Health Economics

Health economics and health economics parameters are not evaluated in this study.

9. Statistical Considerations

The statistical analysis plan will be finalized prior to first participant first visit, and it will include a more technical and detailed description of the statistical analyses described in this section. This section is a summary of the planned statistical analyses of the most important endpoints, including primary and key secondary endpoints.

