9.3. Statistical Analyses

9.3.1. General Considerations

Statistical analysis of this study will be the responsibility of the Sponsor or its designee.

Pharmacokinetic analyses will be conducted on data from all participants who receive at least 1 dose of the investigational product and have evaluable PK data.

Safety analyses will be conducted for all enrolled participants who received study intervention, whether or not they completed all protocol requirements.

Summary statistics, data tabulations, and data graphs will be provided as deemed appropriate.

Additional exploratory analyses of the data will be conducted as deemed appropriate. Study results may be pooled with the results of other studies for safety, immunogenicity, and population PK analysis purposes to avoid issues with post-hoc analyses and incomplete disclosures of analyses.

Handling of missing, unused, and spurious data are addressed prospectively in the overall statistical methods described in the protocol and in the statistical analysis plan, where appropriate. Adjustments to the planned analyses are described in the final clinical study report.

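### Does the unfilled template line in SAP 10.3.2, with no stated method for judging whether 350 mg exposure is linear, call for a change to the plan?

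*SAP*

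**What the plan says.** SAP 10.3.2 is two sentences and a leftover instruction. The first sentence is "No formal statistical analysis is planned for this study"; the rest is "The PK parameters will be listed and summarized by study week using standard descriptive statistics. Insert stats methodology here". SAP 10.1 supplies the statistics: arithmetic mean, SD, median, range and count, with geometric mean and geometric CV added for AUCs and Cmax. Protocol 9.1 has no hypotheses, and Protocol 9.5 says the sample size is not based on power.

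Protocol 4.3, the dose justification, says that exposure "from this study will assess whether this exposure falls within linear or nonlinear exposure range compared with a 700- to 2800-mg dose range". It gives the two ends of the scale. For the low doses in Study AACC: "Doses at or below 3 mg/kg (210 mg) had lower than dose proportional exposure (with half-life ~ 4.7 days". Single doses of 700 to 2800 mg, by contrast, "were shown to be dose proportional (with half-life of 11 days) in Study AACD".

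The opening of Protocol Section 9 says of the SAP that "it will include a more technical and detailed description of the statistical analyses described in this section". Protocol 2.1 gives the study's purpose as dosing "at a 350-mg dose to support dosing regimens in future studies". Protocol 9.3.1 adds: "Study results may be pooled with the results of other studies for safety, immunogenicity, and population PK analysis purposes". Linearity does not appear among the objectives and endpoints in Protocol Section 3 or SAP Section 4.

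**The concern.** A drafting instruction left in the section that covers the primary objective suggests that something was never written. The reader cannot tell from the page whether content was lost or a template line survived. The SAP was to be final before the first participant visit, and SAP Section 12 declares no changes from the protocol.

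The gap seems to matter because Protocol 4.3 states a use for the data that no analysis section takes up. Linearity could be judged on first-dose AUC, steady-state AUC, half-life, clearance or accumulation, and by simple description or by a population PK model. If those measures disagreed, the choice among them would be made after the data were seen, in a study meant to guide later dosing regimens.

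**Working it through.** **1. Is a method missing?** Read without its last line, SAP 10.3.2 says no formal analysis, and listing and descriptive summary by study week. SAP 10.1 says which statistics. That matches Protocol 9.1 and 9.5, and SAP 10.4.13, which plans no inference for safety either. Nothing needed to produce the primary results is absent.

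**2. Does the SAP owe a linearity method?** The promise of more detail in Protocol Section 9 covers the analyses described in that section. The linearity sentence is in Section 4.3, and Section 9 does not mention it. Protocol 4.3 does name the reference dose range, the studies and both half-lives. Only the method of comparison is unstated.

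**3. Can the planned parameters answer the question?** SAP 10.3.1 already lists AUC over 0 to 2 weeks for each period, Period 6 half-life, CLss and accumulation ratios. Inputs from the protocol are half-lives of 4.7 and 11 days, a 14-day interval and 25 completers. One-compartment linear decline is assumed, with r = 2^(−14/t½).

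- 4.7 days: r = 0.127, accumulation 1/(1 − r) = 1.15.
- 11 days: r = 0.414, accumulation 1/(1 − r) = 1.71; the sixth interval reaches 1 − r^6 = 99.5% of steady state.

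The documents give no CV. The 95% interval factor for a geometric mean is exp(± t(0.975, 24) × √ln(1 + CV²) / 5):

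- CV 20%: 0.92 to 1.09
- CV 30%: 0.89 to 1.13
- CV 50%: 0.82 to 1.22

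At CV 50%, the upper limit around 4.7 days is 4.7 × 1.215 = 5.7 days and the lower limit around 11 days is 11 × 0.823 = 9.1 days. The two references are distinguishable on a planned parameter. This ignores uncertainty in the reference values themselves.

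**4. Could the planned parameters contradict each other?** A model can be built in which they do: linear elimination with an 11-day half-life plus a saturable path, dA/dt = −(ln 2/11)A − Vmax·A/(Km + A), with six doses of 350 mg every 14 days. Vmax (mg/day) and Km (mg) are assumed. AUC ratios are dose-normalised; those for 350 mg are against the mean of single 700, 1400 and 2800 mg doses. Half-lives are fitted to Days 5, 8 and 37.

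| Vmax, Km | 350 mg single-dose AUC ratio | Period 5 AUC ratio | Period 6 half-life (days) | 700 : 2800 mg AUC ratio | 700 mg half-life (days) |
|---|---|---|---|---|---|
| Linear only | 1.00 | 0.99 | 11.0 | 1.00 | 11.0 |
| 5, 10 | 0.77 | 0.96 | 4.4 | 0.84 | 5.8 |
| 10, 10 | 0.67 | 0.83 | 1.2 | 0.75 | 1.8 |
| 5, 50 | 0.82 | 0.96 | 6.9 | 0.87 | 7.5 |
| 10, 50 | 0.73 | 0.88 | 4.0 | 0.79 | 4.8 |

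In the second row the Period 6 half-life looks nonlinear (4.4 days) while the Period 5 AUC looks linear (0.96). The last two columns show why this does not carry over to the trial. Protocol 4.3 reports dose proportionality from 700 to 2800 mg and an 11-day half-life. Every saturable row breaks both facts, with AUC ratios of 0.75 to 0.87 and 700 mg half-lives of 1.8 to 7.5 days.

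The 4.4-day figure also comes from one straight line through points that bend: Days 5 to 8 alone give 9.0 days. SAP 10.3.1 starts the terminal phase where systematic departure from log-linear decline ends, and requires a reliable estimate.

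**The case for a change.** The best case for a change is that the leftover line is a plain defect in a final document, and that a stated use of the data deserves a basis named in advance. One sentence would do it, at almost no cost.

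Two cautions behind that case are sound.

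- AUC to infinity after the first dose is planned, but with 14 days of data and an 11-day half-life about 2^(−14/11) = 41% of it is extrapolated, above the 20% at which SAP 10.3.1 flags a value.
- AUC over 0 to 4 weeks should not be set directly against one 700 mg dose. Under fully linear PK at 11 days the Month 1 ratio is (2 + r)/(2(1 + r)) = 0.85, and the Month 3 ratio is [(1 − r^5) + (1 − r^6)]/[2(1 − r²)] = 1.20.

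Both concern interpretation. A pharmacokineticist comparing doses would match the time windows and notice the extrapolation flag. Neither makes a planned parameter or summary wrong.

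A fuller remedy, with several measures side by side, no deciding parameter and no limits, would still leave the reading to judgement and so would not remove the discretion complained of. It would also need concentrations and sampling days from Studies AACC and AACD that these documents do not give. The comparison may belong in the pooled population PK work that Protocol 9.3.1 allows. The table and figure shells mentioned in SAP Section 3 were not available to check.

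**Conclusion.** No change to the plan is needed. The stray line is a clerical slip that can be deleted at the next edit. The documents cannot prove that it is only a template remnant, but the method stated before it is complete for a descriptive study. The unstated comparison method is a gap that analysts can fill sensibly, because the reference range, the half-lives and the relevant parameters are all in the documents.

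The effect on the planned results is nil: no primary parameter, population or summary would differ. The reading of linearity will remain a matter of judgement, as it would with an added sentence.

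This rests on linearity staying outside the objectives and endpoints, and on the half-lives in Protocol 4.3 being a fair guide. The separation of 4.7 from 11 days also assumes about 25 completers and a CV no higher than about 50%. Conflict between the planned measures has not been ruled out, but the cases that produce it contradict the protocol's own reference facts.

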10.4 Safety and Tolerability Assessments

10.4.1 Adverse events

Where changes in severity are recorded in the Case Report Form (CRF), each separate severity of the adverse event (AE) will be reported in the listings, only the most severe will be used in the summary tables. A pre-existing condition is defined as a condition that starts before the participant has provided written informed consent and is ongoing at consent. A non-treatment emergent AE is defined as an AE which starts after informed consent but prior to dosing. A TEAE is defined as an AE which occurs post-dose or which is present prior to dosing and becomes more severe post-dose.

All AEs will be listed. TEAEs will be summarized by severity and relationship to the study drug. The frequency (the number of AEs, the number of participants experiencing an AE and the percentage of participants experiencing an AE) of treatment-emergent AEs will be summarized by Medical Dictionary for Regulatory Activities (MedDRA) (version is documented in the Data Management Plan [DMP]) system organ class and preferred term. The summary and frequency AE tables will be presented for all causalities and those considered related to the study drug by the investigator. Any SAEs and product complaints will be listed. AEs by week of onset will be presented.

Discontinuations due to AEs will be listed.

